4.8.5. Exploration of Bioequivalence between FX006 and TAcS

Bioequivalence (BE) ratios between extended-release FX006 (Test) and immediate-release TAcS (Reference) for C_{max} and AUC parameters will be explored. Bioequivalence between Test and Reference will be evaluated using the average BE method for the mean ratio between test and reference products ($\mu T / \mu R$) as described in FDA guidance for the assessment of bioequivalence (FDA, 2013).

The FDA Guidance on the assessment of Bioequivalence recommends that bioequivalence measures of AUC and C_{max} be log-transformed. In this study, the natural log will be used to transform the values for the model, and the C_{max} , AUC_{0-24} , and $AUC_{0-\infty}$. PK parameters will be exponentiated from a mixed effects model to examine bioequivalence.

In this study bioequivalence is not expected for the ratio of FX006 / TAcS. The properties of FX006 suggest that a reduced C_{max} (reduced maximum exposure) is evident due to slower release of TA into systemic circulation. The potential shift in T_{max} and potential decay in C_{max} , both of which would be associated with corresponding differences in AUC will be explored.

A linear mixed effects model may be used for this study to average bioequivalence with PK parameters of log-transformed AUC_{0-24} , $AUC_{0-\infty}$, and C_{max} . In the initial model fixed effects for treatment and site will be included, with a random effect for patient.

GM with 95% CIs will be presented for each treatment group. BE ratio with standard error (SE) and 90% CIs will be presented for C_{max} , AUC_{0-24} , and $AUC_{0-\infty}$.

4.9. Safety Analyses

Safety analyses will be conducted using the Safety Population.

4.9.1. Adverse Events

Adverse events will be coded using the Medical Dictionary for Regulatory Activities (MedDRA) and displayed in tables and listings using System Organ Class (SOC) and Preferred Term.

Analyses of adverse events will be performed for those events that are considered treatment emergent, where treatment emergent is defined as any adverse event with onset after the administration of study medication in the first knee through the end of the study or any event that was present at baseline but worsened in intensity through the end of the study.

If the start date/time of an AE is partially or completely missing, the date/time will be compared as far as possible with the date/time of the start of administration of study drug. The AE will be assumed to be treatment emergent if it cannot be definitively shown that the AE did not occur or worsen during the treatment-emergent period (worst case approach). The following general rules will be used:

- If the start time of an AE is missing but the start date is complete, an AE will only be excluded as being treatment emergent if the start date is before the date of study drug administration or if the stop date/time is before study drug administration.
- If the start time and day are missing but the start month and year are complete, an AE will only be excluded as being treatment emergent if the start month/year is before the

month/year of study drug administration or if the stop date/time is before study drug administration.

- If the start day and month are missing but the start year is complete, an AE will only be excluded as being treatment emergent if start year is before the year of study drug administration or if the stop date/time is before study drug administration.
- If the start date is completely missing, an AE will be considered treatment-emergent unless the stop date/time is before study drug administration.

Adverse events are summarized by patient incidence rates; therefore, in any tabulation, a patient contributes only once to the count for a given SOC or preferred term.

Adverse events tables and listings will be presented by actual treatment arm.

The number and percentage of patients with any treatment-emergent AE (TEAE), with any serious TEAE, with any TEAE leading to study discontinuation (related or serious), with any TEAE by maximum severity and with any TEAE by relationship will be tabulated.

Similar data presentations will be made for knee related TEAEs. In these tabulations, related is defined as any TEAE deemed possibly, probably or definitely related to study drug by the investigator.

Tabulations presented in SOC internal agreed order and PT in alphabetical order within each SOC will also be produced for:

- all treatment-emergent AEs
- related TEAEs
- TEAEs by maximum severity
- for serious TEAEs

Knee related TEAEs will be tabulated in a similar manner. Knee related TEAEs that occur in both knees will be provided in a separate listing.

No formal hypothesis-testing analysis of AE incidence rates will be performed.

All AEs occurring on-study will be provided in data listings.

By-patient listings will also be provided for the following: patient deaths, Serious Adverse Events (SAE), and AEs leading to discontinuation.

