8.1. Adverse Events

8.1.1. Definitions

An AE is any untoward medical occurrence in a patient or clinical investigation subject administered a pharmaceutical product and that does not necessarily have a causal relationship with this treatment.

An AE can therefore be:

- Any unfavorable and unintended sign (including an abnormal laboratory finding), symptom, or disease temporally associated with the use of a medicinal (investigational) product, whether or not related to the medicinal (investigational) product.
- Any clinically significant abnormality found on an ECG, laboratory test or physical examination.
- Any worsening (i.e., any clinical significant adverse change in frequency and/or intensity) of a preexisting condition, which is temporally associated with the use of the medicinal (investigational) product, is also an AE.

An SAE is any untoward medical occurrence that at any dose:

- Results in death,
- Is life-threatening,
 - This serious criterion refers to an event in which the patient was at substantial risk of death at the time of the event; it does not refer to an event which hypothetically might have caused death if it were more severe.
- Requires inpatient hospitalization or prolongation of existing hospitalization,
 - This serious criterion applies if the reported AE requires at least a 24-hour inpatient hospitalization or, if in the opinion of the Principal Investigator, prolongs an existing hospitalization. A hospitalization for an elective procedure or a routinely scheduled treatment is not an SAE by this criterion because a "procedure" or a "treatment" is not an untoward medical occurrence.
- Results in permanent or significant disability/incapacity, or
 - This serious criterion applies if the "disability" caused by the reported AE results in a substantial disruption of the patient's ability to carry out normal life functions.

- Is a congenital anomaly/birth defect.
 - This serious criterion applies if a patient exposed to a medicinal (investigational) product gives birth to a child with congenital anomaly or birth defect.

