8.1.2. Evaluating and Recording of Adverse Events

At each visit all AEs that occur from the time of treatment and throughout a patient's study participation that are observed, elicited by the site personnel, or reported by the patient, will be recorded in the source documentation and appropriate section of the AE eCRF and evaluated by the Principle Investigator or Sub-Investigator.

Minimum information required for each AE includes type of event, duration (start and end dates), severity, seriousness, causality to investigational medicinal product, action taken, and outcome.

Severity of AEs will be graded by the Principal Investigator using the Common Terminology Criteria for AEs (CTCAE) version 4.0 (refer to the Study Manual or http://ctep.cancer.gov/protocolDevelopment/electronic_applications/ctc.htm).

For AEs not listed in the CTCAE, the following definitions should be used:

| | |
|---------|---|
| Grade 1 | Mild Symptomatic or mild symptoms Clinical or diagnostic observations only Intervention not indicated |
| Grade 2 | Moderate Minimal, local or noninvasive intervention indicated Limiting age-appropriate instrumental activities of daily living (ADL)* |
| Grade 3 | Severe or medically significant but not immediately life-threatening Hospitalization or prolongation of hospitalization indicated Disabling Limiting self-care ADL** |
| Grade 4 | Life-threatening consequences Urgent intervention indicated |
| Grade 5 | Death related to AE |

*Instrumental ADL refer to preparing meals, shopping for groceries or clothes, using the telephone, managing money, etc.

**Self-care ADL refer to bathing, dressing and undressing, feeding self, using the toilet, taking medications, and not bedridden.

The relationship of the AE to the investigational medicinal product should be specified by the Principal Investigator, using the following definitions:

1. Not Related: Concomitant illness, accident or event with no reasonable association with treatment.
2. Unlikely: The reaction has little or no temporal sequence from administration of the investigational medicinal product, and/or a more likely alternative etiology exists.

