9.4.4. Safety Analyses

9.4.4.1. Analysis of Adverse Events

AEs will be coded using the Medical Dictionary for Regulatory Activities (MedDRA) dictionary. Incidences (number and percent) of treatment-emergent adverse events (TEAEs), those events that started after dosing or worsened after dosing, will be presented by treatment group. Incidences of TEAEs will also be presented by maximum severity and relationship to study medication. Similar presentations will be provided for serious AEs, AEs leading to withdrawal from the study, or AEs leading to death. Analysis of AE data will include examination of the incidence rates of TEAEs and index knee related TEAEs.

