2 Visit should be conducted +/- 2 days from scheduled date

3 Consent must be obtained prior to performing any study-specific procedures.

4 Complete assessment prior to dosing.

5 Record any medications received within 30 days prior to Screening.

6 Obtain new x-rays if >6 months since prior x-ray.

7 Both knees will be assessed for tenderness, heat/redness, swelling, effusion, and Baker's cyst. Clinically significant findings (new or worsening from baseline) should be recorded as AEs.

8 Via Central Laboratory

- 9 Conduct for females of childbearing potential only. Serum pregnancy test to be performed via central laboratory at Screening and End-of-Study visit (scheduled for Day 43); urine pregnancy test to be performed locally on Day 1 and results available prior to dosing.
- 10 On Day 1, blood for plasma drug concentration measurements will be collected prior to dosing and at Hours 1, 2, 3, 4, 5, 6, 8, 10, and 12 post-injection of the first knee (\pm 10 minutes).
- 11 On Day 2, blood for plasma drug concentration measurements will be collected at 24 hours post-injection of the first knee (\pm 2 hours), and on subsequent visits as convenient.
- 12 Blood for morning cortisol measurements will be collected between 7 and 9 am.
- 13 The injection of the second knee should take place within 15 minutes of the first knee injection.
- 14 AEs and Concomitant Medications will be captured from Day 1 (post-injection) to End of Study Visit.

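### SAP 4.9.1 keeps worsened events in principle, but its rules for incomplete start dates can exclude them, and it counts worsening in intensity only, which is narrower than the protocol

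*SAP*

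**What the plan says.** Protocol 9.4.4.1 describes TEAEs as "those events that started after dosing or worsened after dosing". Protocol 8.1.1 treats the worsening of a pre-existing condition as an AE and explains worsening as "any clinical significant adverse change in frequency and/or intensity".

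SAP 4.9.1 has two limbs. On onset, "treatment emergent is defined as any adverse event with onset after the administration of study medication in the first knee", with the window closing at study end. On worsening, it adds "any event that was present at baseline but worsened in intensity through the end of the study". Frequency is not mentioned.

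The SAP then gives rules that apply "If the start date/time of an AE is partially or completely missing". An introductory sentence states a worst-case principle: the event is treatment-emergent unless it can be shown that it neither occurred nor worsened in the treatment-emergent period. Four rules follow.

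- **Rule 1** (date complete, time missing): "an AE will only be excluded as being treatment emergent if the start date is before the date of study drug administration", or if the event stopped before dosing.
- **Rules 2 and 3** have the same structure, with a pre-dose month and year, or a pre-dose year, in place of the date.
- **Rule 4** (start date wholly missing) excludes only on a pre-dose stop.

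SAP section 5 lists one departure from the protocol, the sort order of listings.

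**The concern.** The definition and the worst-case sentence both look at worsening. Rules 1 to 3, which a programmer would code, do not. An event's start date says nothing about whether it later worsened, so a pre-dose start alone should not settle the matter. The intensity limit is a second, separate narrowing of the protocol.

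Safety and tolerability form one of the two primary objectives, and they are read largely from the TEAE and knee-related TEAE tables. Inclusion requires symptoms in both knees for at least 6 months, so a flare after injection may well be a worsening of something already present. Any misclassification from these two gaps lowers the reported incidence.

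**Working it through.** The plan has no stated figure to reproduce here. The check sets the texts side by side for each way a worsened pre-existing condition could be recorded.

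| Record | TEAE under the protocol | SAP definition | SAP rules for incomplete start |
|---|---|---|---|
| A. Worsening entered as its own AE, start date after dosing | Yes | Yes (onset limb), for intensity or frequency | Not excluded |
| B. Original record, pre-dose start date and time both known, worse in intensity | Yes | Yes (worsening limb) | Do not apply |
| C. Original record, pre-dose start date known but time missing (or only a pre-dose month/year or year known), worse in intensity | Yes | Yes (worsening limb) | Rules 1 to 3 allow exclusion |
| D. Original record, pre-dose start, worse in frequency only | Yes | No | Do not apply if date and time are known; rules 1 to 3 allow exclusion if partial |
| E. Original record, start wholly missing, worse in intensity | Yes | Yes (worsening limb) | Rule 4 keeps it unless it stopped before dosing |

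**Internal contradiction.** B and C are the same clinical event. B is counted, and C can be excluded only because the clock time is absent. E, with less information than C, is kept. Nothing in the worst-case sentence supports that ordering.

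**Departure from the protocol.** D is a TEAE under the protocol and not under the SAP definition.

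**How often rule 1 might apply.** Protocol 8.1.2 says "Minimum information required for each AE includes type of event, duration (start and end dates", followed by severity, seriousness, causality, action taken and outcome. Start time is not in that list, so a complete date without a time may be common. The list is a minimum and the eCRF is not among the documents, so this is a possibility only.

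**What a pre-dose start means here.** SAP 2.4, Table 1, footnote 14 states: "AEs and Concomitant Medications will be captured from Day 1 (post-injection) to End of Study Visit". Data errors aside, an AE record with a pre-dose start is then most naturally a pre-existing condition reported because it worsened.

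**Scale.** SAP 2.1 plans about 24 patients allocated 1:1, so about 12 per arm. One patient whose only TEAE is dropped changes that arm's incidence by 1/12 = 0.083, or 8.3 percentage points.

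**The case against.** The strongest reply is that the protocol's recording rules lead to record A. Sections 7.9.3 and 7.9.5 send findings present before dosing to medical history and make new or worsened post-dose findings AEs. Section 8.1.5 reports a change from baseline status as an AE, and collection starts after injection. On that reading the AE is the worsening itself, dated after dosing, and neither gap loses anything. This stands as the more natural reading, but no passage says which start date to enter for a worsened condition. The SAP's own worsening limb is needed only if some records carry an onset before dosing.

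A reader might infer that the SAP treats every AE with a pre-dose start as not treatment-emergent. The text does not support that. The rules cover only incomplete start dates or times, they state when an event may be excluded rather than must be, and they sit under a principle that keeps worsened events. What remains is a contradiction within 4.9.1, with literal coding of the rules giving the wrong answer for record C.

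A reader might also take the arthralgia rate in protocol 5.2.7 (9.8%; 0.098 × 12 = 1.18 patients per arm) and infer that an arm's arthralgia incidence could fall from about 10% to zero. That rate is for any joint, after a single injection at any dose, pooled across studies. It does not measure worsened pain in a treated knee over 6 weeks, and the inference also needs every site to enter the original onset.

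On frequency, it is fair that 8.1.1 defines an AE rather than a TEAE, and that the minimum AE data include severity but no frequency item. Protocol 9.4.4.1 nevertheless says worsened without qualification, so the SAP is still narrower.

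Finally, AE rates are descriptive, with no hypothesis test, and all on-study AEs are listed, so an omitted event would be visible in a trial of this size. That limits the harm but does not correct the tables.

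**Conclusion.** Wrong as written; a minor-to-moderate consistency correction. Two things follow from the text alone: rules 1 to 3 contradict the SAP's own definition and worst-case principle on worsened events, and the intensity limit narrows the protocol without being declared.

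Whether any event is lost depends on how sites date worsened conditions, and for record C also on whether the start time or part of the date is missing. The documents settle neither. The effect ranges from nothing, if every worsening is entered under its own date, to the loss of all such events, if every one keeps its original onset and meets one of the two gaps. The 8.3 points per patient is a yardstick, not an estimate, and applies only where the dropped event was that patient's sole TEAE. The direction is known: TEAE and knee-related TEAE incidence can only be understated by these gaps.

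**What to change.** In SAP 4.9.1:

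1. Change the worsening limb to read *worsened in frequency and/or intensity after dosing*, in line with protocol 8.1.1 and 9.4.4.1.
2. In rules 1 to 3, make a pre-dose start date, month/year or year a ground for exclusion only if the event also did not worsen after dosing. The pre-dose stop condition stays as it is.

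It would also help to state in the eCRF guidance which start date is entered for a worsened condition, since that decides whether the gaps matter. If the sponsor does intend the narrower definition, it belongs in SAP section 5 as a declared change.

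The cost is wording, with no new analysis. TEAE counts may rise slightly, and a mis-dated pre-dose event may occasionally be counted, which is consistent with the SAP's worst-case approach.

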4.9.2. Laboratory Data

Clinical laboratory values will be expressed in SI units.

The actual value and change from baseline (Day 1 or Screening if Day 1 is missing) will be summarized for each hematology and clinical chemistry laboratory parameter by actual treatment arm. In the event of repeat values, the last non-missing value per study day/time will be used.

All laboratory data will be provided in data listings.

4.9.3. Vital Signs and Physical Examinations and Knee Assessment

The actual value and change from baseline (Day 1) at each time point will be summarized for vital signs by actual treatment arm. Vital sign measurements will be presented for each patient in a data listing.

All physical examination abnormalities will be presented in a data listing.

The incidence of inflammation, as determined from the knee assessment, will be tabulated for each visit. For those patients experiencing inflammation, the details of the inflammation will also be tabulated. In these tabulations, percentages will be based on those patients who have a non-missing knee assessment at a given visit. In addition, a shift table displaying shifts in knee assessments from baseline over time will be presented. Knee assessment as well as knee aspiration data will be presented in a data listing. Inflammation data will be summarized separately for each knee with the first and second knee defined as stated previously.

4.9.4. Electrocardiogram

ECG data will be provided in patient data listing.

4.9.5. Concomitant Medications

Concomitant medications will be defined as those medications that were initiated after first dose of treatment or those that were ongoing at the time of first study drug administration. If the start date or stop date of a medication is partially missing, the date will be compared as far as possible with the date of the start of administration of study drug. The medication will be assumed to be prior medication if it cannot be definitively shown that the medication did not start or continue during the treatment period. The following approach will be taken:

- If the start date of medication is complete and occurs on or after the day of the first dose, the medication will be assumed concomitant. If the start date occurs prior to the first dose date but the end date is on or after the first dose date or the medication is recorded as ongoing, the medication will be considered concomitant.
- If the start day is missing but the start month and year are complete, a medication will only be excluded as being concomitant if the start month/year is before the month/year of study drug administration and if the stop date (full date, month and year if missing day, or year if missing month and day) is before study drug administration.
- If the start day and month are missing but the start year is complete, a medication will only be excluded as concomitant if the start year is before the year of study drug administration and if the stop date (full date, month and year if missing day, or year if missing month and day) is before study drug administration.
- If the start date is completely missing and the stop date is prior to first dose or completely missing, the medication will be assumed to be a prior medication.

The use of concomitant medications and pain/restricted medications will be included in a by-patient data listing. Pain/restricted medications are specifically identified in the CRF and will be noted in the listing.

5. CHANGES TO PLANNED ANALYSES

Although the protocol states that listings will be provided by study site and patient, per this SAP, by-patient listings will be sorted by treatment arm and then patient number.

7. CLINICAL STUDY REPORT APPENDICES

7.1. Statistical Tables to be Generated

Table 14.1.1	Patient Enrollment and Disposition
Table 14.1.2	Demographic and Baseline Characteristics (Safety Population)
Table 14.1.3	Osteoarthritis History and Bilateral Knee Characteristics (Safety Population)
Table 14.1.4	Summary of Protocol Deviations (Safety Population)
Table 14.1.5	Study Drug Exposure Summary (Safety Population)
Table 14.1.6	Summary and Change from Baseline for Serum Cortisol (nmol/L) by Visit (Safety Population)
Table 14.1.7	Plasma Drug Concentrations (pg/mL) by Time Point (PK Population)
Table 14.2.1	Plasma Pharmacokinetic Parameters (PK Population)
Table 14.2.2	Summary of Bioequivalence Geometric Mean Ratios (PK Population)
Table 14.3.1.1	Summary of Treatment-Emergent Adverse Events (Safety Population)
Table 14.3.1.2	Treatment-Emergent Adverse Events by System Organ Class and Preferred Term (Safety Population)
Table 14.3.1.3	Treatment-Emergent Adverse Events by System Organ Class and Preferred Term - Related to Study Drug (Safety Population)
Table 14.3.1.4	Treatment-Emergent Adverse Events by System Organ Class and Preferred Term by Maximum Severity (Safety Population)
Table 14.3.1.5	Knee-Related Treatment-Emergent Adverse Events by System Organ Class and Preferred Term (Safety Population)
Table 14.3.1.6	Knee Related Treatment-Emergent Adverse Events by System Organ Class and Preferred Term- Related to Study Drug (Safety Population)
Table 14.3.1.7	Knee Related Treatment-Emergent Adverse Events by System Organ Class and Preferred Term by Maximum Severity (Safety Population)
Table 14.3.1.8	Serious Adverse Events by System Organ Class and Preferred Term (Safety Population)
Table 14.3.2.1	Patient Listing of Deaths
Table 14.3.2.2	Patient Listing of Serious Adverse Events
Table 14.3.2.3	Patient Listing of Discontinuations Due to Adverse Events
Table 14.4.1.1	Summary and Change from Baseline for Hematology Parameters by Visit (Safety Population)
Table 14.4.1.2	Summary and Change from Baseline for Chemistry Parameters by Visit (Safety Population)
Table 14.4.2	Summary and Change from Baseline for Vital Signs by Visit (Safety Population)
Table 14.4.3	Summary of Bilateral Knee Assessments (Safety Population)

